8.4 Evaluation of Response

Response assessment is for measuring time to disease progression. Time point response assessments will be performed on Cycle 4 Day 1 and Treatment discontinuation (timed to coincide with mid-point and the end of study) with a confirmatory assessment (required for non-randomized trials) within 6 weeks after a PR or CR is deemed. Response assessment may also be based on tumor marker measurements. To determine time point response using imaging studies, refer to **Table 5** and below.

Table 5. Time Point Response Criteria (+/- non-target disease)

Target Lesions	Non-Target Lesions	New Lesions	Overall Response
CR	CR	No	CR
CR	Non-CR/Non-PD	No	PR
CR	Not evaluated	No	PR
PR	Non-PD or not all evaluated	No	PR
SD	Non-PD or not all evaluated	No	SD
Not all evaluated	Non-PD	No	NE
PD	Any	Yes or No	PD
Any	PD	Yes or No	PD
Any	Any	Yes	PD

Table 6. Time Point Response Criteria (non-target disease only)

Non-Target Lesions	New Lesions	Overall Response
CR	No	CR
Non-CR/non-PD	No	Non-CR/non-PD ¹
Not all evaluated	No	NE
Unequivocal PD	Yes or No	PD
Any	Yes	PD

1 Non-CR/non-PD is preferred over SD for non-target disease since SD is used as endpoint for assessment of efficacy in trials so to assign this category when no lesions can be measured is not advised.

The best overall response is the best response recorded from the start of study treatment until end of treatment (taking into account any requirement for confirmation). In general, the patient's best response assignment will depend on the achievement of both measurement and confirmation criteria and will be determined by combining the patient's status of target lesions, non-target lesions, and new lesions.

- **Residual Disease:** Patients with objective response but who continue to have residual measurable disease.
- **Symptomatic Deterioration:** Patients with global deterioration of health status requiring discontinuation of treatment without objective evidence of disease progression at that time, and not related to study treatment or other medical conditions should be reported as progressive disease due to "symptomatic deterioration." Every effort should be made to document objective progression even after discontinuation of treatment due to symptomatic deterioration. Symptomatic deterioration that may lead to discontinuation of treatment include, but is not limited to, symptoms such as:
 - Weight loss > 10% of body weight.
 - Worsening of disease-related symptoms (e.g., worsening dyspnea, increasing pain/increasing requirement for narcotic analgesics).

- Decline in performance status of > 1 level on ECOG scale.

8.5 Guidelines for Evaluation of Measurable Disease

All measurements should be taken and recorded in metric notation. All baseline evaluations should be performed as closely as possible to the beginning of treatment and never more than 4 weeks before the beginning of the treatment.

The same method of assessment and the same technique should be used to characterize each identified and reported lesion at baseline and during follow-up. Imaging-based evaluation is preferred to evaluation by clinical examination unless the lesion(s) being followed cannot be imaged but are assessable by clinical exam.

- **Clinical Lesions:** Clinical lesions will only be considered measurable when they are superficial (e.g., skin nodules and palpable lymph nodes) and ≥ 10 mm diameter as assessed using calipers (e.g., skin nodules). In the case of skin lesions, documentation by color photography, including a ruler to estimate the size of the lesion, is recommended.
- **Chest x-ray:** Lesions on chest x-ray are acceptable as measurable lesions when they are clearly defined and surrounded by aerated lung. However, CT is preferable.
- **Conventional CT and MRI:** This guideline has defined measurability of lesions on CT scan based on the assumption that CT slice thickness is 5 mm or less. If CT scans have slice thickness greater than 5 mm, the minimum size for a measurable lesion should be twice the slice thickness. MRI is also acceptable in certain situations (e.g., for body scans).

Use of MRI remains a complex issue. MRI has excellent contrast, spatial, and temporal resolution; however, there are many image acquisition variables involved in MRI, which greatly impact image quality, lesion conspicuity, and measurement. Furthermore, the availability of MRI is variable globally. As with CT, if an MRI is performed, the technical specifications of the scanning sequences used should be optimized for the evaluation of the type and site of disease. Furthermore, as with CT, the modality used at follow-up should be the same as was used at baseline and the lesions should be measured/assessed on the same pulse sequence. It is beyond the scope of the RECIST guidelines to prescribe specific MRI pulse sequence parameters for all scanners, body parts, and diseases. Ideally, the same type of scanner should be used and the image acquisition protocol should be followed as closely as possible to prior scans. Body scans should be performed with breath-hold scanning techniques, if possible.

- **PET CT:** At present, the low dose or attenuation correction CT portion of a combined PET-CT is not always of optimal diagnostic CT quality for use with RECIST measurements. However, if the site can document that the CT performed as part of a PET-CT is of identical diagnostic quality to a diagnostic CT (with IV and oral contrast), then the CT portion of the PET-CT can be used for RECIST measurements and can be used interchangeably with conventional CT in accurately measuring cancer lesions over time. Note, however, that the PET portion of the CT introduces additional data which may bias an Investigator if it is not routinely or serially performed.
- **Ultrasound:** Ultrasound is not useful in assessment of lesion size and should not be used as a method of measurement. Ultrasound examinations cannot be reproduced in their entirety for

independent review at a later date and, because they are operator dependent, it cannot be guaranteed that the same technique and measurements will be taken from one assessment to the next. If new lesions are identified by ultrasound in the course of the study, confirmation by CT or MRI is advised. If there is concern about radiation exposure at CT, MRI may be used instead of CT in selected instances.

- **Endoscopy, Laparoscopy:** The utilization of these techniques for objective tumor evaluation is not advised. However, such techniques may be useful to confirm complete pathological response when biopsies are obtained or to determine relapse in trials where recurrence following complete response (CR) or surgical resection is an endpoint.
- **Tumor Markers:** Tumor markers alone cannot be used to assess response. If markers are initially above the upper normal limit, they must normalize for a patient to be considered in complete clinical response.
- **Cytology, Histology:** These techniques can be used to differentiate between partial responses (PR) and complete responses (CR) in rare cases (e.g., residual lesions in tumor types, such as germ cell tumors, where known residual benign tumors can remain).

The cytological confirmation of the neoplastic origin of any effusion that appears or worsens during treatment when the measurable tumor has met criteria for response or stable disease is mandatory to differentiate between response or stable disease (an effusion may be a side effect of the treatment) and progressive disease.

- **FDG-PET:** While FDG-PET response assessments need additional study, it is sometimes reasonable to incorporate the use of FDG-PET scanning to complement CT scanning in assessment of progression (particularly possible 'new' disease). New lesions on the basis of FDG PET imaging can be identified according to the following algorithm:
 - Negative FDG-PET at baseline, with a positive FDG-PET at follow-up is a sign of PD based on a new lesion.
 - No FDG-PET at baseline and a positive FDG-PET at follow-up: If the positive FDG-PET at follow-up corresponds to a new site of disease confirmed by CT, this is PD. If the positive FDG-PET at follow-up is not confirmed as a new site of disease on CT, additional follow-up CT scans are needed to determine if there is truly progression occurring at that site (if so, the date of PD will be the date of the initial abnormal FDG-PET scan). If the positive FDG-PET at follow-up corresponds to a pre-existing site of disease on CT that is not progressing on the basis of the anatomic images, this is not PD.
 - FDG-PET may be used to upgrade a response to a CR in a manner similar to a biopsy in cases where a residual radiographic abnormality is thought to represent fibrosis or scarring. The use of FDG-PET in this circumstance should be prospectively described in the protocol and supported by disease-specific medical literature for the indication. However, it must be acknowledged that both approaches may lead to false positive CR due to limitations of FDG-PET and biopsy resolution/sensitivity.

Note: A ‘positive’ FDG-PET scan lesion means one which is FDG avid with an uptake greater than twice that of the surrounding tissue on the attenuation corrected image.

9 SAFETY EVALUATION

9.1 Adverse Events

9.1.1 Definition

An adverse event or adverse experience (AE) is any untoward medical occurrence associated with the use of a drug in humans, whether or not considered drug related. Therefore, an AE can be ANY unfavorable and unintended sign (including an abnormal laboratory finding), symptom, or disease temporally associated with the use of a medicinal (investigational) product, whether or not considered related to the medicinal (investigational) product (attribution of ‘unrelated’, ‘unlikely’, ‘possible’, ‘probable’, or ‘definite’).

An AE is considered “unexpected” if it is not listed in the investigator brochure or is not listed at the specificity or severity that has been observed; or if an investigator brochure is not required or available, is not consistent with the risk information described in the general investigational plan in other study-related documents.

9.1.1.1 Diagnosis Versus Signs and Symptoms

If known, a diagnosis should be recorded on the CRF rather than individual signs and symptoms (e.g., record only liver failure or hepatitis rather than jaundice, asterixis, and elevated transaminases). However, if a constellation of signs and/or symptoms cannot be clinically characterized as a single diagnosis or syndrome at the time of reporting, each individual event should be recorded as an AE or SAE on the CRF. If a diagnosis is subsequently established, it should be reported as follow-up information.

9.1.1.2 Adverse Events Occurring Secondary to Other Events

In general, AEs occurring secondary to other events (e.g., cascade events or clinical sequelae) should be identified by their primary cause. For example, if severe diarrhea is known to have resulted in dehydration, it is sufficient to record only diarrhea as an AE or SAE on the CRF.

However, clinically significant AEs occurring secondary to an initiating event that are separated in time should be recorded as independent events on the CRF. For example, if a severe gastrointestinal hemorrhage leads to renal failure, both events should be recorded separately on the CRF.

9.1.1.3 Abnormal Laboratory Values

Only clinically significant laboratory abnormalities that require active management will be recorded as AEs or SAEs on the CRF (e.g., abnormalities that require study drug dose modification, discontinuation of study treatment, more frequent follow-up assessments, further diagnostic investigation, etc.).

If the clinically significant laboratory abnormality is a sign of a disease or syndrome (e.g., alkaline phosphatase and bilirubin 5 x the upper limit of normal associated with cholecystitis), only the diagnosis (e.g., cholecystitis) needs to be recorded on the Adverse Event CRF.

If the clinically significant laboratory abnormality is not a sign of a disease or syndrome, the abnormality itself should be recorded as an AE or SAE on the CRF. If the laboratory abnormality can be characterized by a precise clinical term, the clinical term should be recorded as the AE or SAE. For example, an elevated serum potassium level of 7 mEq/L should be recorded as “hyperkalemia”

Observations of the same clinically significant laboratory abnormality from visit to visit should not be repeatedly recorded as AEs or SAEs on the CRF, unless their severity, seriousness, or etiology changes.

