1.6.2.4 INCB024360 Clinical Studies

INCB24360-101 has been evaluated in Phase I study conducted by Incyte Corporation in subjects with refractory solid tumors. The study has used a 3+3 dose escalation design, with doses of INCB024360 ranging from 50 mg once daily (QD) to 700 mg twice daily (BID). Three subjects have initiated treatment at 50 mg QD, 4 subjects at 50 mg BID, 3 subjects at 100 mg BID, 6 subjects at 300 mg BID, 11 subjects at 400 mg BID, 5 subjects at 500 mg BID and 4 subjects at 700 mg BID.

INCB024360 has generally been well tolerated. The most common Grade 1 or Grade 2 AEs in $\geq 20\%$ reported have been fatigue, nausea, decreased appetite, vomiting, constipation, abdominal pain, diarrhea, dyspnea, back pain, and cough. The most common Grade 3 or Grade 4 AEs were

abdominal pain, hypokalemia, and fatigue (9.6% each). Despite 1 patient reporting a dose-limiting toxicity (DLT) of radiation pneumonitis at 300 mg BID, additional subjects were enrolled at this dose and no additional DLTs were reported. At 400 mg BID, 1 patient reported a DLT of Grade 3 fatigue, with no additional DLTs at this dose level. Another patient at 400 mg BID developed asymptomatic and transient hypopituitarism after 1 cycle of therapy and was able to continue dosing with INCB024360. Among the 18 subjects treated at either 600 mg or 700 mg BID, no DLTs were observed. Dose escalation was completed based on preliminary pharmacokinetic and pharmacodynamic data, which demonstrated that doses of INCB024360 above 300 mg BID achieved exposures exceeding the IC90 determined in nonclinical models and, in pharmacodynamic assays, reached a plateau for Kyn/Trp levels and ratios. In the final cohort of 600 mg BID, the effect of food on INCB024360 absorption was evaluated. No objective responses were reported. At 2 months, stable disease was seen in 15 patients and lasted \geq 4 months in 7 patients. The main AE reported in subjects receiving more than 2 cycles of INCB024360 has been Grade 1 or Grade 2 fatigue.

In a combination study conducted by Incyte Corporation of INCB024360 and ipilimumab in metastatic melanoma patients, 5 of 7 subjects enrolled at a dose of 300 mg BID of INCB024360 plus 3 mg/kg of ipilimumab, developed Grade 3 or Grade 4 AST and ALT elevations between 2 and 4 cycles of treatment. Only one of these subjects had a bilirubin elevation of Grade 1.

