6.3 Dose Modification

No dose adjustments during this study are planned for the DEC205mAb-NY-ESO-1 fusion protein (CDX-1401) given with adjuvant poly-ICLC vaccine.

In the event of excessive discomfort, skin breakdown or desquamation, or a Grade 3 treatment-related systemic toxicity following CDX-1401 and poly-ICLC dosing, administration of adjuvant (poly-ICLC) on the subsequent day should be omitted. Provided the toxicity has resolved to Grade 2 or less, the next monthly treatment may be administered as scheduled at a new administration site.

Refer to **Section 11.1** for the Phase I parameters and decisions rules for INCBO24360 dose adjustments.

Dose adjustments for hematological toxicity will be based on the blood counts obtained at baseline and after each 28-day cycle of DEC205mAb-NY-ESO-1 fusion protein (CDX-1401) given with adjuvant poly-ICLC and with or without INCBO24360.

If at least 2/3 or 2/6 DLT's are observed in cohort one, the dose of INCBO24360 will be reduced from 300 mg to 100 mg BID. If at least 2/3 or 2/6 DLT's are observed in Cohort 1, the dose of INCBO24360 will be reduced from 100 mg to 50 mg BID in Cohort 2. The study will continue at this dose level.

Dose modification for INCBO24360 are based on decision rules in **Section 11.1**.

Patients will be withdrawn from the study if they fail to recover to Grade 2, CTCAE Version 4.0, from a treatment-related toxicity within 4 weeks (leading to treatment delay of \geq 4 weeks. For patients that recover in $<$ 4 weeks, when toxicities have resolved to Grade 2 or lower, INCBO24360 may be restarted. In patients that recover from toxicity in less than 4 weeks and who restart therapy, the next treatment cycle will be scheduled for 4 weeks later. Additional cycles will also follow at 4 weeks intervals.

Dose modification for Phase IIB (INCBO24360 cohorts)

When an INCBO24360 toxicity is observed, dose administration may be delayed/interrupted to allow for recovery from toxicity. INCBO24360 may be restarted at a reduced dose of 100 mg. po BID. Please contact the PI for attribution.

Based on the phase I safety review, INCBO24360 300 mg. po BID x 7 cycles has been selected for the phase IIB dose. Dose modification criteria will be defined as any Grade 3 or higher treatment-related (i.e. definitely, probably, or possibly related) toxicity that occurs outside the DLT evaluation period including:

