- Febrile neutropenia with standard of care treatment for \geq 7 days. Growth factors may be used according to American Society of Clinical Oncology guidelines.
- Platelets \leq 50 \times 10⁹/L
- Grade 3 or greater non-hematologic toxicity
- Serum bilirubin $>$ 3.0 mg/dL
- AST / ALT $>$ 3.5 x ULN
 - AST normal range: 15 U/L – 46 U/L
 - ALT normal range: 11 U/L - 66 U/L
- Serum creatinine $>$ grade 3 (equal or greater) will be considered a DLT
- Grade 3 or greater hypersensitivity reaction. If the hypersensitivity reaction is determined to be related to INCBO24360 alone, the INCBO24360 will be discontinued and patient may continue on treatment with CDX-1401 with Poly-ICLC at the discretion of the investigator.

Dose modification for exploratory cohort with Sirolimus (Roswell site ONLY):

Based on the completed trial (I 191511 “A Phase 1 Clinical Trial of mTOR Inhibition With Rapamycin for Enhancing Intranodal Dendritic Cell Vaccine Induced anti-Tumor Immunity In Patients with NY-ESO-1 Expressing Solid Tumors”), the 4 mg/day Sirolimus dose was safely used in combination with DEC205 and therefore dose modification is not expected. However, in the event of an unexpected toxicity attributed to Sirolimus, a lower dose of Sirolimus may be considered.

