11.3 Toxicity

All patients enrolled in this study will be eligible for the analysis of toxicity.

The toxicity rate will be estimated using a one-sided, 95%, exact binomial confidence interval (Clopper-Pearson). The lower one sided limit will be used.

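### After the 28-day DLT window, recording a Phase IIb hepatic laboratory rise as an adverse event rests more on investigator discretion in Cohort 2a than in 2b, so AE-based hepatic rates by arm may not be comparable

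*Combined protocol and SAP*

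**What the plan says.** Section 9.1.1 counts any unfavourable sign, including an abnormal laboratory finding, as an adverse event. Section 9.1.1.3 is narrower: "Only clinically significant laboratory abnormalities that require active management will be recorded as AEs or SAEs on the CRF". Its first example is "abnormalities that require study drug dose modification", followed by "discontinuation of study treatment, more frequent follow-up assessments, further diagnostic investigation, etc".

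Section 6.3 says of the vaccine: "No dose adjustments during this study are planned for the DEC205mAb-NY-ESO-1 fusion protein (CDX-1401) given with adjuvant poly-ICLC vaccine". Its Phase IIb dose-modification text is for the INCB024360 cohorts. The criteria there are Grade 3 or higher treatment-related toxicities outside the DLT evaluation period, and the list includes "AST / ALT $>$ 3.5 x ULN" and bilirubin above 3.0 mg/dL. Table 1 shows that Cohort 2a receives the vaccine and adjuvant only, and Cohort 2b adds INCB024360. Section 3.1 describes the study as open-label.

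For analysis, Section 11.3 states: "The toxicity rate will be estimated using a one-sided, 95%, exact binomial confidence interval (Clopper-Pearson"), using the lower limit. It does not say how laboratory toxicity is counted or that the rate is given by arm. Section 11.5 says that safety will be evaluated by obtaining, reviewing and analysing data that include changes in laboratory values, but specifies no grading or tabulation by arm.

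**The concern.** Section 1.6.2.4 gives the reason to look at liver enzymes: in an earlier study of INCB024360 with ipilimumab, 5 of 7 subjects at 300 mg BID "developed Grade 3 or Grade 4 AST and ALT elevations between 2 and 4 cycles of treatment". Cohorts 2a and 2b are the trial's randomised view of what INCB024360 adds to the vaccine, including any hepatic toxicity.

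For that view to be fair, a given laboratory value should have the same chance of being counted in either arm. Here the route onto the AE form runs through management, and the plan sets out more laboratory-triggered management for one arm than for the other. The investigator who decides on the remaining actions knows the assignment. A recorded excess in Cohort 2b could then partly reflect recording. At stake are the arm-level rates, any descriptive comparison, and the safety data that the monitoring committee reviews annually.

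**Working it through.** The plan gives no figure to reproduce. The check sets the rules side by side, for a hepatic laboratory rise after the 28-day DLT window.

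| Route to the AE form | Cohort 2b | Cohort 2a |
|---|---|---|
| INCB024360 delay, interruption or reduction (6.3, Phase IIb) | Listed for AST/ALT above 3.5 x ULN or bilirubin above 3.0 mg/dL, if judged treatment-related; wording is permissive | None |
| Omission of Day 2 poly-ICLC after Grade 3 treatment-related systemic toxicity (6.3) | Available | Available |
| Withdrawal if a treatment-related toxicity does not recover to Grade 2 within 4 weeks (6.3) | Available | Available |
| Study pause for any Grade 4 event (6.3.2) | Available | Available |
| Extra follow-up, work-up, stopping treatment, other (9.1.1.3) | Investigator discretion | Investigator discretion |

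1. **Threshold.** Section 6.3 states upper normal limits of 46 U/L (AST) and 66 U/L (ALT). The criterion is therefore 3.5 x 46 = 161 U/L and 3.5 x 66 = 231 U/L. After Day 28 these values are a listed reason to modify treatment in Cohort 2b and in Cohort 2a are not.

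2. **DLT window.** Section 6.3.1 applies the same AST/ALT and bilirubin limits to toxicity related to the study drugs, for 28 days after the first vaccine dose, and a DLT ends treatment. If that applies to both Phase IIb arms, there is little asymmetry inside the window. As far as Table 3 can be read, however, the first chemistry panel after baseline is on Cycle 2 Day 1, that is Day 1 + 28 = Day 29 (within 3 days). Most scheduled hepatic values therefore fall after the window. So did the ipilimumab combination signal, which arose between 2 and 4 cycles.

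3. **Other shared rules.** Table 3 shows no Day 2 chemistry, so a scheduled liver value will seldom inform the omission of Day 2 adjuvant. The withdrawal and Grade 4 rules act on persistent or severe events. A rise above the limit that is below Grade 4 and resolves is left, in Cohort 2a, mainly to discretion.

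4. **Size.** Let p be an arm's true rate of such rises and c the fraction recorded. The expected recorded count is 25 x p x c. With equal p, the ratio of expected recorded counts, 2b to 2a, is c(2b)/c(2a). The documents give neither fraction, and if they are equal there is no distortion.

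5. **Sensitivity of the planned statistic.** If Section 11.3 is applied to one arm of 25, each unrecorded patient lowers the observed rate by 1/25 = 4 percentage points. The exact one-sided 95% lower limit is 8.2% for 5/25, 5.7% for 4/25 and 1.4% for 2/25. These counts show how much a few patients matter; they are not estimates of what will be missed.

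**The case against.** The strongest reply is that the management list in 9.1.1.3 is open-ended and that extra follow-up, diagnostic work-up and discontinuation count in either arm. For a Cohort 2a value above 3.5 x ULN to go unrecorded, it must be neither rechecked nor worked up. The omission, withdrawal, DLT and Grade 4 rules are not limited to INCB024360 either. All of this stands, and it narrows the gap. It does not close it, because the discretionary triggers are applied by an unblinded investigator and only Cohort 2b has a written hepatic criterion after Day 28.

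Four stronger readings are tempting and should be resisted:

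- **The same rise is counted in 2b and missed in 2a.** The documents do not say so. Section 6.3 says that INCB024360 may be delayed, and its criteria require attribution to treatment, so recording in 2b is partly discretionary too.
- **A specific inflation of the risk ratio.** Any such figure restates an assumed recording fraction in 2a and assumes complete recording in 2b. Neither is in the documents.
- **The plan ignores laboratory values apart from AEs.** Section 11.5 names analysis of changes in laboratory values. What is missing is a graded table by arm.
- **The same argument for blood counts.** Section 6.3 bases haematological dose adjustments on counts taken with or without INCB024360. That sits badly with its statement that no vaccine adjustment is planned. The two statements must be reconciled before an arm difference can be argued for haematology.

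It is also fair to say that Section 11 states no between-arm toxicity test, that the Phase IIb primary endpoint is PFS, and that the hepatic signal comes from 7 patients given a different partner drug.

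**Conclusion.** The concern holds in a limited form. After the 28-day DLT window, recording a hepatic laboratory rise as an adverse event depends more on investigator discretion in Cohort 2a than in Cohort 2b, so AE-based hepatic rates may not be comparable between arms. Under-recording in 2a is possible, not automatic, and its size cannot be derived from the documents. No planned test is affected; arm-level rates, descriptive comparison and monitoring committee review are.

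This rests on reading 9.1.1.3 as the operative rule despite the wider definition in 9.1.1, and on Section 6.3 giving Cohort 2a no hepatic criterion of its own in Phase IIb. Priority is modest, between optional and advisable. The case for acting is mainly that the remedy is cheap.

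**What to change.** Add to Section 11.3, for Phase IIb:

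- CTCAE v4.0 grades will be derived directly from the scheduled laboratory values, at least AST, ALT, bilirubin, creatinine, platelets and blood counts, whether or not an AE was entered.
- Worst post-baseline grade, shift from baseline, and the number of patients beyond the limits already listed in Section 6.3 will be tabulated by arm, with the number tested at each visit. Those limits serve only as cut-points for the table.
- The table will cover visits scheduled in both arms, at least Cycle 2 Day 1 to Cycle 5 Day 1. Vaccine runs for 5 cycles and INCB024360 for 7, so later values should be shown separately. Unscheduled rechecks should stay out of the comparison, because their frequency can depend on the arm.
- Laboratory toxicity rates will be based on this table and not on the AE form.

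Section 9.1.1.3 need not change for this. Separately, the two Section 6.3 statements on haematological dose adjustment and on no vaccine adjustment should be reconciled; no clinical rule is proposed here.

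The cost is a few lines of text and a little more analysis work, with no new sampling or staff, provided the scheduled values are entered in the database. Laboratory toxicity rates may come out higher than those on the AE form, and the report should say why.
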